2.4.3.3 Observation session

Observations will be undertaken by one or more trained researchers, who will act as non-participant observers. They will position themselves to be able to discreetly observe a group of patients whose vital signs observations will fall due, or else discreetly shadow a nurse who is about to undertake a vital signs observation round. We will adapt tools and techniques from the HS&DR funded 'CLECC' study [25] and Wong et al.[26] Data will be recorded on a tablet device using software designed for recording nurse patient interactions on wards (QITool) with records taken at both the session level and the 'interaction' level (in this case a set or group of vital signs measurements). For each observation session we will record the number of patients and the number and grades (RN band 5 and above, HCA and other assistant staff

band 1-4) of all nursing care staff on the ward. For each patient whose vital signs are recorded we will assign a session-specific identifier and record basic details that can be discerned from distant observation, such that would be available to any visitor to the ward (for example position and the presence of visitors). The type of staff taking vital signs measurements will be recorded and categorised (e.g. registered nurse, care assistants).

We will record start and finish times for both vital signs rounds and individual vital signs measurements. For a vital signs 'round' an interaction record will be opened with a start time recorded when the nurse begins to assemble the necessary equipment and ended when the nurse moves away from the patient bed space and engages on another task (i.e. other than taking vital signs measurements from the next patient) unrelated to vital signs measurements. Therefore, each set vital signs measurements will be clustered with a vital signs 'round' which will include one of more sets of vital signs measurements. Observation sessions will continue for 2 hours with observer discretion to extend the session if the required number of vital signs measurements have not been recorded.

Observers will not intervene in care but should they observe practice that risks causing the patient harm they will alert the nurse in charge.

2.4.3.4 Sample size

Based on the standard errors of mean times observed in the study by Wong et al.[26] (a study with a similar clustering structure), the minimum sample size that would be acquired (640 sets of observations) would allow us to estimate a mean observation time with a precision of approximately +/- 10%. This precision will be increased by including more vital signs observations if this proves feasible within the scheduled observation 'budget' and, as we have more clusters and fewer observations per cluster than the Wong study, this is likely to be a conservative estimate of precision.

2.4.3.5 Observer training

The observer will be trained prior to undertaking observations using protocols and training material from Wong et al[26] and the QITool. We will also undertake intermittent reliability tests to ensure there is no deterioration in observer performance over time. Although we cannot easily discount the effects of observers on nurses' performance of vital signs measurements, we will seek to undertake observations in as unobtrusive fashion as possible and emphasise to participating staff that we are not evaluating their practice.

It seems most likely that observer effects will increase diligence, which may lead to increased estimates of the time taken to obtain vital signs measurements. For those hospitals using electronic vital signs recording, we will analyse the routine data obtained from the retrospective analysis, by looking for evidence that incomplete observations were less frequent during observation periods. We will consider the potential implications of any observer effects through sensitivity analysis in our economic modelling

2.4.3.6 Data analysis

We aim to estimate the time taken to undertake vital signs observations and to understand systematic sources of variation that may influence the 'burden' of vital signs observations. We will determine the extent to which estimates of time taken

are sensitive to predictable factors and use this as the basis of a sensitivity analysis when estimating associated costs.

Our data will consist of a series of interactions that represent a complete set of vital signs measurements. Measurements will be grouped into rounds, where one or more sets of vital signs observations and associated actions are recorded. Additionally, there may be other actions associated with vital signs measurement that we are not able to record because they do not occur within vital signs rounds.

We will estimate the time taken for vital signs measurement in 2 ways.

- Average time to take a set of observations (based on individual sets of measures)
- ii) Average length of vital signs rounds / number of sets of vital signs measurements taken with the round

We will use multilevel mixed-effects models to determine the influence of patient, nurse, ward and hospital factors on the length of observation. Factors considered will include the average number of measurements taken in a round in order to identify efficiencies that may be associated with undertaking formal observation rounds. The coefficients from these models will be used to estimate adjusted (conditional) mean work (time) associated with taking observations based upon these factors. We will use our stakeholder consultations (see main protocol) in order to identify whether any further allowances should be added to estimated times based on unobserved work associated with vital signs measurements. These factors and the differences between estimated values will be used in sensitivity analyses in the economic analysis (below)

2.4.3.7 Data management

The QITool provides a platform for data recording with automated secure upload to a central server. This server and the associated databases are located at and managed by the IT team of the University of Southampton. Both the tablet, the data transfer and the centrally stored files are encrypted with password protected access available to members of the project team and database managers only. No personal data is stored or transferred. All data will be retained as part of a central database with extracts made for analysis for this study. These extracts will be processed on individual staff computers and may be shared more widely across the project team but will always be stored on password protected and encrypted machines. Again, no personal data will be contained within these files and codes identifying wards and trusts will be stored separately and are only accessible by the project team. These codes, which link back to wards, will be erased at the earliest possible opportunity, depending upon the requirements of other regulatory approvals and (for example) requirements to report accruals to the CRN Portfolio.

2.4.3.8 Malpractice

While undertaking observations of nursing staff measuring patients' vital signs, the delivery of an unacceptable standard of clinical practice may become apparent or be strongly suspected by one or more members of the research team. Such incidents will be classified as either sub-optimal or unsafe practice.

2.4.3.8.1 Sub-optimal practice

Observers may witness events which they do not consider represent 'best practice', but which do not pose a direct and immediate risk to patients or others. In such

circumstances researchers will use a 'manager test' in order to determine how to proceed.

The manager test: If the researcher were working clinically as a registered practitioner in the clinical setting and observed the incident in question (incompetence, misconduct or other unsafe practice), is it of such severity that they would they feel obliged to report the incident to the manager of the individual involved? If yes, this is defined as unsafe practice, and the guidelines below would be followed. If no, no further action would be taken.

2.4.3.8.2 Unsafe practice

This is defined for the purposes of this study as incompetence, misconduct or other unsafe practice that a registered practitioner would feel obliged to report to the manager of the individual involved if working in a practice capacity. (Note this is a higher test than whether a professional would simply discuss the incident with that person directly). This will include any behaviour that is clearly illegal or dangerous, placing individuals at direct risk of harm.

Unsafe practice is likely to be a very rare occurrence. If it does occur, the research team member will take the following actions:

If unsafe practice is observed/suspected during an observation:

- 1. Halt the observation.
- 2. Explain to the staff member that the practice must be reported due to its potentially serious nature and it may not be possible to maintain anonymity.
- 3. Outline the process for doing this (use local Trust reporting system).
- 4. Terminate the observation session and follow the guidelines below.
- 2.4.3.8.3 Guidelines for taking further action:
- The patient/visitor/staff member is given the required time and support and empathic approach to the issue.
- The patient/visitor/staff member is given a thorough explanation of the course of action required to ensure the event is fully investigated and acted upon.
- The patient/visitor/staff member is treated with respect and dignity at all times.
- The researcher maintains responsibility for keeping the patient/visitor/staff member informed and involved where appropriate, until the incident is reported to senior trust personnel.
- The patient/visitor/staff member is offered support and guidance in line with research governance.
- The researcher collates the necessary information from the patient/visitor/staff member to report to the most appropriate senior personnel in order to take further action.

Although this response would breach the assumption of confidentiality, it is considered that the potential benefit to others should outweigh the desirability of maintaining anonymity

2.4.4 Generating putative monitoring protocols

In the later stages of the project, the findings from the observational studies and stakeholder consultations will be brought together to create and validate protocols. The primary outcome of WP2 will be a data-driven schedule for monitoring patients'

vital signs, based on their current acuity. Using estimates from our state-space models we will explore the following:

- 1. Given a level of physiological abnormality what is the average chance that this value will be higher at any given point of time in the future?
- 2. Given a level of physiological abnormality, what is the average chance that an adverse event will occur at any given point of time in the future?

We will explore grouping patients using early warning scores (e.g. NEWS, CEWS). We aim to identify points in time where there is a significant risk that patients' vital signs have changed adversely. We will manually inspect these to look for threshold effects across time. For example, for low-acuity patients who deteriorate (i.e. increase in acuity), what is the earliest point in the future that this could be detected? A limitation of the study is that we can only explore average rates of deterioration, as we do not have access to data on interventions or individual diagnoses. However, we will explore how our estimates change in subsets of patients (e.g. elective surgery, emergency surgery and medicine). Exploring the data in this way will permit us to propose different monitoring schedules, designed to increase the likelihood that a new vital signs observation picks up deterioration if and when it happens.

We will also undertake a variety of computer simulation studies, where estimates from our models are used to simulate the performance of current monitoring protocols (e.g. those proposed by the RCP[1]) and our new ones. This will allow us to quantify: (a) the number of observations required; and (b) the risk that deterioration will be missed.

The estimates obtained from WP3 will then be used to model the marginal costs and consequences for all protocols whose performance is equivalent to or exceeds that of the current NEWS protocol for detecting deterioration. In addition, we will model potential reductions in mortality and changes in ICU use (e.g. admission/acuity at admission/length of stay) associated with improved detection. Finally, stakeholders will be consulted to review the protocols and comment on their likely effectiveness.

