2.2.2.2 Implications for staff resources

Whereas under-observation can delay the opportunity to detect patient deterioration and initiate remedial treatment[8], [9], over-observation uses valuable nursing resources that could be better deployed to other essential aspects of patient care. Indeed, compliance with current monitoring protocols is often poor, with many observations missed or delayed[11]–[14]. This is particularly evident at night[12], [23], [24], when staffing is at its lowest. Preliminary results from our current HS&DR "Missed Care" study (ISRCTN: 17930973) show that compliance with vital signs observations is significantly (p<0.05) associated with the level of available nursing staff. Estimates of the time required to take observations are scarce, but a survey of 2917 registered nurses across 46 acute hospitals in England showed that one-third had felt unable to undertake all necessary patient surveillance due to lack of time on their last shift[15]. However, even when staffing is sufficient, there are valid clinical reasons why nursing staff will deviate from protocols. Therefore, it is essential to have a monitoring protocol that is achievable on the ward and does not compromise other aspects of care.

With this in mind, and by adapting techniques from our previous work[15], [25], [26], part of this study will be a prospective observation of recording vital signs across a range of wards. This will allow us to understand better the impact on staff workload and factors that might affect compliance with patient surveillance.

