2.4.1.4 Data analysis

Intermittent observations of vital signs show some specific features that should be properly accounted for in any modelling framework. They are longitudinal in nature, i.e. multiple observations are taken over the same sample unit (patients) over time, and are multivariate as multiple variables (e.g. pulse, blood pressure) are jointly measured at each observation time. These data also show serial dependence and high correlation between measurements within patients. A natural way to account for these features is to use State Space Models (SSMs), as they provide a framework of flexible time-dependent models. SSMs cast multivariate distributions (see [44] for a review), accounting for the serial dependence, heterogeneity between patients, and transitions between states that depend on other covariates. We will use this modelling approach to estimate changes in vital signs over time and the probability of adverse events (e.g. in-hospital mortality, unanticipated ICU admission, cardiac arrest).

Our reference modelling setting will be the multivariate Hidden Markov Model (HMM)[45], a well-known type of SSM. Its use is justified by its versatility and mathematical tractability:

- the availability of all moments
- the likelihood computation is linear with respect to the number of observations;
 the marginal distributions are easy to determine and missing observations can be handled with minor effort
- the conditional distributions are available, outlier identification is possible, and forecast distributions can be calculated

For vital signs data collected during routine monitoring on the ward, there are additional clinical processes that have the potential to introduce bias our analysis. Firstly, these data have been collected in the context of existing monitoring protocols, where the time to the next observation is determined by an early warning score (NEWS[1], [5], Portsmouth; CEWS[43], Oxford). Secondly, previous work[12] by our group and others shows that in practice, nursing staff often undertake "observation rounds", in the early mornings and evenings. These observations result in deviations from the patient-specific schedule dictated by the early warning score. Thirdly, there will be observation sets taken when patients report additional symptoms or are deemed to "look unwell"; information that will not captured in available variables in our data set.

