We will estimate costs for regimens assuming full compliance and partial compliance based on currently observed rates. As we know that compliance with vital signs observations is highly correlated with the scheduled frequency we will use adjusted and unadjusted rates such that (for example) we assume that 80% of all observations are taken under both old and new regimes (unadjusted) or we stratify estimated compliance by observation frequency so that (for example) 100% of 12 hourly observations are taken whereas 50% of 4 hourly observations are taken. As a secondary analysis we will also consider changes in staff skill mix, for example if a new regime increases the number of observations then we might assume that all additional observations are undertaken by Band 2 HCA.

Cost differences will be calculated by determining the difference in cost between two regimes. Marginal consequences will be estimated differences in resource use (time and grade/type of staff conducting observations and follow-up). We will derive estimates of possible benefits (e.g. reduced mortality, length of stay in ICU) by relating the time of detection of deterioration associated with a given monitoring protocol, to coefficients derived from published studies that report the benefits of early detection and/or increased frequency of observations[51]–[54]. The incremental benefits of each proposed protocol will be compared to the incremental staffing costs and a cost per life saved estimated. We will also estimate QALYS on the assumption that life expectancy and quality of the 'lives saved' will be similar to that of the group of patients who died using standard estimates of QALE adjusted for patient demographic factors[55]. If reductions in ICU admissions, hospital stay or other resource use are identified as outcomes these will also be considered in the estimated cost differences. These will be costed using Department of Health Reference Costs 2015-2016 (or latest available update).

All variables included in the economic analysis are estimated subject to (parameter) uncertainty, while model type, the models and assumptions made in building them are subject to methodological and structural uncertainties. We will address methodological and structural uncertainty through scenario analyses testing the robustness of the results to model type, scope and other key structural assumptions. Parameter uncertainty will be addressed through deterministic sensitivity analyses

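### Schedules are simulated with rates from patients who were managed once deterioration was recorded, so the penalty of a longer interval is likely understated; the direction depends on how a missed deterioration is defined

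*Protocol*

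**What the plan says.** Protocol section 2.4.4 plans simulation studies in which "estimates from our models are used to simulate the performance of current monitoring protocols (e.g. those proposed by the RCP[1]) and our new ones". The outputs are "a) the number of observations required; and (b) the risk that deterioration will be missed"; what counts as missed is not defined. Protocols that perform at least as well as the current NEWS protocol go on to costing.

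The same section states that "we do not have access to data on interventions or individual diagnoses". It presents this as restricting the study to average rates and answers it with subsets of patients.

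Section 2.4.1.4 acknowledges that "these data have been collected in the context of existing monitoring protocols", and adds two further sources of bias: observation rounds, and sets taken because a patient looks unwell. Its response is to let changes between mixture components depend on time to next observation and time of day.

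Section 2.4.5 obtains mortality and ICU benefits by "relating the time of detection of deterioration associated with a given monitoring protocol" to coefficients from published studies.

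**The concern.** Section 2.2.2.2 gives the reason for monitoring: "under-observation can delay the opportunity to detect patient deterioration and initiate remedial treatment". On the protocol's own account, then, a patient's course is expected to change once deterioration is found. Rates estimated from routine data mix the course before and after that change.

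Simulating a schedule with a different interval needs the course of a patient who has worsened and has not yet been found. If the mixed rates are used instead, that simulated patient recovers partly as if already treated, and may have fewer adverse events than an untreated patient would.

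The simulation decides which schedules are costed, and its detection times feed the estimated benefits, cost per life saved and QALYs. A distortion here reaches the study's main comparison.

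**Working it through.** **Do the planned safeguards separate treated from untreated course?** The three biases in section 2.4.1.4 and the two covariates all concern when a patient is observed. None is a term for care after a finding. The subgroup analyses (2.4.1.4, 2.4.4) and the Oxford validation (2.2.3) use the same kind of monitored and managed patients, so agreement there would not reveal the problem. The scenario analyses in 2.4.5 belong to the economic model and do not mention recovery that depends on detection.

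The protocol gives no figure to reproduce on this point, and no recovery or event rates. Everything below rests on assumed rates. The 12 h and 4 h intervals appear in the protocol as examples and are used only as illustration.

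**Check 1: delay from onset to detection.** Assume onset uniform within an interval of length D and an exponential episode with mean m, ignoring adverse events.

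- Mean delay among episodes found: m − D·exp(−D/m) / (1 − exp(−D/m)).
- With no recovery until found: D/2, so 6.0 h and 2.0 h, a contrast of 4.00 h.
- Example, m = 6 h: D = 12 gives 6 − 12 × 0.1353/0.8647 = 4.12 h; D = 4 gives 6 − 4 × 0.5134/0.4866 = 1.78 h. The contrast is 2.34 h, and 1 − 2.34/4.00 is about 41%.

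| Assumed m (h) | Delay, 12 h | Delay, 4 h | Contrast | Understated against 4.00 h |
|---|---|---|---|---|
| 3 | 2.78 | 1.57 | 1.21 | 70% |
| 6 | 4.12 | 1.78 | 2.34 | 41% |
| 12 | 5.02 | 1.89 | 3.13 | 22% |
| 24 | 5.50 | 1.94 | 3.56 | 11% |

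**Check 2: episodes that end unseen.** In the same model this proportion is 1 − (m/D)(1 − exp(−D/m)). For m = 6 h it is 57% at 12-hourly and 27% at 4-hourly. For m = 3, 12 and 24 h the pairs are 75% and 45%, 37% and 15%, and 21% and 8%. With no recovery until found it is 0% at both. On this metric, treated recovery makes the longer interval look worse.

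**Check 3: adverse events before the next set.** Data were generated from a Markov model with four states (stable, deteriorated and undetected, deteriorated and treated, adverse event). Stable patients were observed every 4, 6 or 12 h and deteriorated patients every 1 or 4 h. A model without treatment information was fitted by maximum likelihood, and its rates were used to predict risk over one interval. Onset was 0.02 per hour throughout.

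| Scenario | Recovery per h, untreated / treated | Event per h, untreated / treated | Event risk at 12 h, true / simulated | Simulated share of the extra event risk per hour, 12 h over 4 h |
|---|---|---|---|---|
| No effect | 0.10 / 0.10 | 0.02 / 0.02 | 1.76% / 1.76% | 1.00 |
| Mild | 0.05 / 0.10 | 0.02 / 0.01 | 2.06% / 1.42% | 0.64 |
| Moderate | 0.05 / 0.20 | 0.02 / 0.01 | 2.06% / 1.51% | 0.58 |
| Strong | 0.02 / 0.20 | 0.02 / 0.005 | 2.29% / 1.38% | 0.46 |
| Recovery only | 0.02 / 0.20 | 0.01 / 0.01 | 1.19% / 1.12% | 0.71 |
| Events only | 0.05 / 0.05 | 0.03 / 0.01 | 2.99% / 1.59% | 0.54 |

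In the moderate case the fitted recovery rate was 0.197 per hour, close to the treated 0.20 and far from the untreated 0.05.

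Two exceptions matter. With an effect on recovery only, absolute event risk was overstated at 4 h and 8 h (ratios 1.33 and 1.10), because the fitted onset rate also rises. And on the resolved-unseen metric the moderate case at 12 h gives 4.7% true against 18.2% simulated, the reversal seen in check 2.

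**The case against.** **The model lets the course vary with the interval.** A reader might infer that the simulated course is identical under every schedule and that event rates cannot differ. The documents do not support that, because section 2.4.1.4 allows transitions to depend on time to next observation. What remains is narrower: in these data the interval was set by the score, so an association with the interval reflects how ill the patient was and is not the effect of being found.

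**The direction is not fixed.** A reader might also infer that long intervals must look safer. That fails if missed counts episodes resolving unseen, as check 2 shows, and this part of the objection stands in full. It also rules out a simple remedy that reruns the simulation with recovery switched off and asks each schedule to match the benchmark both ways. On the resolved-unseen metric every schedule would then score zero, and the rule would separate nothing.

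**The limitation is disclosed and the results are provisional.** Section 2.4.4 states the lack of intervention data, and 2.4.5 plans scenario analyses and says its cost-effectiveness estimates would need validating in a trial. That lowers the stakes, but the limitation is not carried into the simulation that selects schedules.

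**Benefits come from published coefficients.** This is true, so the harm of delay is not simply removed. The coefficients are still applied to simulated detection times, and the distortion enters there.

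**Simulation detail may sit in a SAP.** Detail can be left there. The protocol itself, however, fixes the source of the rates and the selection rule while stating that the data needed to separate the two courses are absent.

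**Conclusion.** The concern holds in a conditional form. The rates that drive the schedule comparison are those of patients managed after detection, and nothing planned separates treated from untreated course. If care after detection is effective, the simulated penalty of a longer interval is likely understated when measured as onset-to-detection delay or as adverse events before the next set. If missed means an episode that resolves unseen, the bias reverses.

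The size for this study is unknown. The 70% to 11% range rests on assumed treated means of 3 to 24 h, is taken among episodes found, and compares with an extreme in which nobody recovers untreated. The shares of 0.46 to 0.71 for extra event risk rest on assumed rates and a model simpler than the planned one. Both show direction and plausible order, not an estimate. Because simulated performance decides which schedules are costed, the sponsor should act on this.

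**What to change.** In section 2.4.4:

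1. Define the performance metric on a delay or harm scale, such as time from onset to the first set taken in the worse state, or an adverse event before the next set. Do not define it as episodes ending unseen. If delay is used, say how episodes that end before any set are counted.
2. State that the estimated rates apply under existing monitoring and response.
3. Add a sensitivity simulation in which, until the first simulated set that finds the patient in the worse state, recovery is slowed across a range down to none and the event rate is raised across a stated range.
4. Report whether the ranking of schedules against the benchmark is unchanged, and carry both sets of detection times into the scenario analyses of section 2.4.5.

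The cost is extra simulation runs and additional result columns; no new data are needed. The downside is that the no-recovery end is a bound and not a best estimate, since some episodes resolve untreated, and it should be labelled so.
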